## Power calculations

Using the method of Hussey and Hughes (2007), power was calculated based on 19 sites and 7 study waves (with the number of sites per wave as above), and with 4 months between waves. Calculations assumed that the average number of patients seen in a site during a month was 1,205 patients, based on 2014 data for these sites. We assumed the following pre-implementation rates for the main study outcomes based on KPWA screening data from 2012 and treatment data from 2014:

- Alcohol brief intervention outcome (defined as the proportion of primary care patients seen in the clinic who screened positive for unhealthy alcohol use and were given a brief intervention): 34.2 per 10,000 patients seen ( $0.342\% = 19\% \text{ screened} \times 36\% \text{ screened positive} \times 5\% \text{ brief intervention}$ ). Note that the estimated percentage of patients who receive brief intervention is unknown, and the value of 5% used here is thought to be an upper bound.
- NCQA treatment outcome (defined as the proportion of primary care patients seen in the clinic who initiated and engaged in treatment): 3.9 per 10,000 ( $0.039\% = 1.26\% \text{ newly diagnosed} \times 37.5\% \text{ initiating treatment} \times 8.2\% \text{ engaged}$ ).

To account for within-site correlation of patient outcomes, we further assumed a value for the intraclass correlation coefficient (ICC) of 0.001, equal to the observed ICC for AUD diagnosis rates across these sites for a 6-month period based on 2014 data. Note that these calculations assume that the ICC is constant over time, and that the correlation of patients from the same clinic at different time points is the same as for patients from the same clinic at the same time point (Hemming, Taljaard, and Forbes 2017). Power was calculated based on a two-sided test and a type 1 error rate of 0.05.

Based on these calculations, we expect to have 80% (90%) power to detect an increase in brief intervention rates of 7.1 (8.2) per 10,000 patients seen and an increase in the treatment outcome of 2.6 (3.1) per 10,000 patients seen. The following table shows power at other effect sizes:

Outcome	Assumed effect size: change in number (per 10,000 patients seen) before vs. after implementation	Power
Brief Intervention	6	0.67
	8	0.89
	10	0.97
Treatment	2	0.60
	3	0.89
	4	0.98

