level. All outcomes are evaluated at the clinic level. A stepped-wedge design, with sites randomly assigned to seven staggered waves, was selected because all clinics needed to receive the SPARC implementation intervention. The objectives of the SPARC trial are to test whether the multi-faceted approach to implementation increases the proportion of PC patients who:

- 1) Screen positive for unhealthy alcohol use and have documented brief interventions, and
- 2) Have AUDs identified and subsequently initiate and engage in treatment for AUDs.

Methods/design

Setting

The trial is conducted in the 22 PC clinics of KPWA, which includes all PC clinics that did not participate in the three-clinic SPARC pilot study [62]. Prior to SPARC implementation, the health system had no population-based preventive SBI (e.g., when measured at three clinics, 8.9% of patients were screened for unhealthy alcohol use) [62], and of an estimated 381,550 total patients who received care at KPWA in 2014, only an estimated 0.04% per year were engaged in AUD care based on the International Classification of Diseases codes, 9th edition (ICD-9) used by the National Committee for Quality Assurance (NCQA) Healthcare Effectiveness Data and Information Set (HEDIS) measures for Alcohol and Drug Use Disorders.

SPARC intervention

Context

Behavioral health integration added to SPARC

At the time the intervention was designed, SPARC clinical care was to be implemented alone to address unhealthy alcohol use. However, at the request of KPWA clinical leaders, parallel care for depression, suicidality, cannabis use, and other drug use was implemented at the same time and supported by the study, because the health system had no population-based screening and systematic follow-up for these conditions [62]. Thus, while this report focuses on alcohol-related care, which is the focus of the SPARC trial, the trial is evaluating implementation of alcohol-related care in the context of simultaneous implementation of a wholistic Behavioral Health Integration program. Table 1 shows the parallel tools and services for each condition.

Table 1 Clinical care implemented in the 22 PC clinics as part of behavioral health integration

Condition	Screen	Assess	Manage
SPARC clinical care			

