Samples and time intervals. A population-based denominator is used in all analyses as the least-biased denominator because clinical site implementation of the SPARC and Behavioral Health Integration interventions is expected to change the proportion and characteristics of patients screened, the proportion who screen positive for unhealthy alcohol use, and the proportion and characteristics of those diagnosed with AUDs. Unless otherwise specified, the sample for each measure is the set of patients who have a PC visit to a PC clinical site for any reason during each

time interval used in analyses. Time intervals used in analyses are typically 4 weeks (i.e., 28-day intervals before and after each clinic's specified launch date). This interval is selected to provide adequate numbers of outcomes per interval [62]. Specifically, primary analyses will compare the monthly (28-day) proportion of patients with each outcome in the pre- versus post-implementation periods.

Statistical analysis

Main analyses of the trial compare two primary outcomes—alcohol SBI and AUD treatment—among PC patients seen in the participating PC clinics before and after the randomized SPARC launch (Fig. 2 and Table 4). Primary analyses will compare the monthly outcome rates of the two primary outcomes before and after launch. Secondary analyses will also compare primary outcomes across other study phases (Fig. 2 and Table 4).

Table 4 The primary analysis

Primary analyses compare months before vs. months after the assigned launch date (usual care + preparation phases vs. active implementation + sustainment phases).
Secondary analyses
a. Usual care vs. active implementation
b. Usual care vs. sustainment
c. Active implementation vs. sustainment

Analyses will follow the general framework for analyzing data from a stepped-wedge trial [70, 71]. The intervals used in analyses are 28-day periods (“month” hereafter) before and after the launch date for each clinic. Specifically, we will model indicator variables for the primary outcomes monthly (e.g., indicator for whether each patient who had a PC visit that month received alcohol SBI or a new AUD diagnosis and treatment) using the following logistic mixed-effect model:

$$\text{logit } P(Y_{ijm} = 1) = \alpha + \beta Int_{jm} + \gamma S_j + f(cm) + b_j + u_i,$$

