## Stepped-wedge trial design

To evaluate the effectiveness of the SPARC implementation, we are conducting a pragmatic stepped wedge trial in 22 KPWA clinics. The trial design (**Figure 1**) addressed several practical concerns of the health system while maintaining a rigorous evaluation of SPARC. The 22 clinics were randomized into 7 mutually exclusive groups of clinics (referred to as “waves”). Here we briefly summarize the features of the design; more detailed explanations for these requirements are described in the protocol paper (Glass et al. 2018):

- A few pairs of clinics were clustered together into larger single clinical sites for the purpose of receiving the SPARC implementation. This resulted in 19 distinct clinical sites, hereafter referred to as “sites.”
- The health system provided input on implementation timing by conducting a stratified randomization on the year of the implementation; the health system identified 9 sites that would be randomized in Year 1 (3 sites in each of 3 waves), and the remaining 10 sites that would be randomized in Years 2-3 (in two waves of 3 sites each and two waves of 2 sites each). We will refer to sites randomized in Year 1 as Y1 sites and sites randomized in Years 2-3 as Y2 sites.
- It was desired that one of the Y2 sites be in a wave with just a single other site
- It was desired that the final wave consist of only 2 sites.

For each wave, there was a 2-month preparatory period prior to the “launch date” of the 4-month period of active implementation. The “launch date” was specified at the time of randomization to study

		Intervention time point								
		Wave	0	1	2	3	4	5	6	7
Y1	1									
	2									
	3									
	4									
	5									
	6									
	7									

**Figure 1:** Schematic illustrating the stepped wedge design, in which 19 sites were divided into 7 waves (2-3 sites per wave) and stratified across two groups (Y1 and Y2). Gray squares denote time periods in which the SPARC implementation was to be implemented based on randomization, which includes the active implementation period and the sustainment period (defined below).

wave. It was the date when each site was intended to start Behavioral Health Integration screening for all patients who came to the site.

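### The treatment base rate of 3.9 per 10,000 is used per 28-day month but is probably an annual figure; if so, the smallest detectable relative effect is larger than the stated power implies

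*SAP*

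**What the plan says.** The SAP (Power calculations) sets the usual-care rate for the second primary outcome as "NCQA treatment outcome (defined as the proportion of primary care patients seen in the clinic who initiated and engaged in treatment): 3.9 per 10,000". It is built as 1.26% newly diagnosed × 37.5% initiating × 8.2% engaging. The stated sources are "KPWA screening data from 2012 and treatment data from 2014". No period is attached to the 1.26% or to the product.

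The same section assumes that "the average number of patients seen in a site during a month was 1,205 patients", with an ICC of 0.001. It reports 80% (90%) power for an increase of 2.6 (3.1) per 10,000, and power of 0.60, 0.89 and 0.98 at increases of 2, 3 and 4. The Protocol (Statistical power) repeats the base rate and the detectable increases.

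The analysis unit is a month: the Protocol (Samples and time intervals) says "primary analyses will compare the monthly (28-day) proportion of patients with each outcome".

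The Protocol (Setting) also describes engagement in AUD care before the trial. It says that "of an estimated 381,550 total patients who received care at KPWA in 2014", "only an estimated 0.04% per year were engaged in AUD care", on ICD-9 codes used for the HEDIS measures.

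**The concern.** A 2014 engagement rate of 0.039% appears in the power calculation without a period, and a 2014 engagement rate of 0.04% appears in the Setting section as annual. Both rest on NCQA measures. The Protocol (AUD treatment) notes that NCQA's own measure takes the first AUD diagnosis in each calendar year, so an annual rate is the natural product of such data.

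The unit matters because numerator and denominator behave differently. A new diagnosis in this trial needs 365 days without an AUD diagnosis, so a patient can become a case about once a year. The same patient enters the denominator in every month with a visit. An annual rate per patient therefore has to be divided by the number of months seen before it is a rate per patient-month.

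Treatment is one of two primary outcomes, and its test is of a log odds ratio. At rates this low the odds ratio is close to the ratio of rates. A null result will be read against the stated power, so the relative effect that the trial could detect should be right.

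**Working it through.** **Inputs.** Sites and waves: "power was calculated based on 19 sites and 7 study waves". Sites per wave are 3, 3, 3, 3, 3, 2, 2 (SAP, Stepped-wedge trial design), giving eight 4-month periods. Patients per site-period: 4 × 1,205 = 4,820. ICC 0.001; two-sided 0.05.

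**Step 1: reproduce the plan.** The Hussey–Hughes variance of the effect is

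Var = I·s²(s² + T·τ²) / [(I·U − W)·s² + (U² + I·T·U − T·W − I·V)·τ²]

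with I = 19 and T = 8. Here U is the number of treated site-periods, W the sum over periods of squared treated counts, and V the sum over sites of squared treated counts.

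- U = 21+18+15+12+9+4+2 = 81
- W = 0+9+36+81+144+225+289+361 = 1,145
- V = 3(49+36+25+16+9) + 2·4 + 2·1 = 415
- The two brackets are 394 and 1,828.

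The variance is taken at the mean of the before and after rates, p̄. So s² = p̄(1−p̄)/4,820 and τ² = 0.001/0.999 × p̄(1−p̄).

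For 3.9 rising by 2.6 per 10,000: p̄ = 0.00052, s² = 1.078×10⁻⁷, τ² = 5.202×10⁻⁷, SE = 0.938 per 10,000, and 2.6/0.938 = 2.77. Power = Φ(2.77 − 1.96) = 0.79.

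| Quantity | Stated | Recomputed |
|---|---|---|
| Treatment, 80% / 90% detectable | 2.6 / 3.1 | 2.63 / 3.12 |
| Treatment, power at 2, 3, 4 | 0.60, 0.89, 0.98 | 0.593, 0.880, 0.979 |
| Brief intervention, 80% / 90% detectable | 7.1 / 8.2 | 7.07 / 8.24 |
| Brief intervention, power at 6, 8, 10 | 0.67, 0.89, 0.97 | 0.668, 0.883, 0.973 |

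Taking 1,205 patients per 4-month period gives 5.89 and 7.11 for treatment, which does not fit. The 3.9 was therefore applied to each patient-month.

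**Step 2: compare the two rates.** 1.26% × 37.5% × 8.2% = 0.0387%, which rounds to the Setting section's 0.04%.

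**Step 3: what a monthly reading would imply.** With k = 2 to 4 (assumed), 1.26% newly diagnosed per month is 1.26 × 2 = 2.5% to 1.26 × 4 = 5.0% newly diagnosed per year, in a system that the Protocol describes as having no population-based preventive screening and brief intervention. Likewise 3.9 per 10,000 per month would be 0.08% to 0.16% per year, two to four times the Setting figure.

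**Step 4: if 3.9 is annual.** The monthly base rate is 3.9/k. Re-solving with everything else unchanged (k = 1 is the plan as written):

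| k (assumed) | Base per 10,000 | 80% detectable | 90% detectable | Power for absolute +2.6 |
|---|---|---|---|---|
| 1 | 3.9 | 2.63 (+68%) | 3.12 (+80%) | 79% |
| 1.5 | 2.60 | 2.22 (+85%) | 2.64 (+102%) | 89% |
| 2 | 1.95 | 1.98 (+101%) | 2.36 (+121%) | 94% |
| 3 | 1.30 | 1.69 (+130%) | 2.03 (+156%) | 97% |
| 4 | 0.975 | 1.52 (+156%) | 1.84 (+188%) | 99% |

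The stated 2.6 is 2.6/3.9 = 67% of the assumed base rate.

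**The case against.** The plan's arithmetic is correct as it stands; the issue is the unit of one input. Four points on the other side carry weight.

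- **The link is inferred.** Neither document says that 3.9 per 10,000 and 0.04% per year are the same quantity. The latter is rounded (0.035% to 0.045%), and its denominator is all KPWA patients rather than primary care patients at these sites. The only period that the SAP attaches to 2014 AUD data is six months, for the ICC. A six-month base rate would also need converting, but by a different factor.
- **Event counts do not rule out a monthly 3.9.** The sites hold 19 × 1,205 × 12 = 274,740 patient-months a year, so 3.9 per 10,000 implies about 107 events. System-wide, 381,550 × 0.0004 is about 153. The 107 fits inside the 153. For k = 2 to 4, however, the sites hold about 137,000 to 69,000 people, and reaching 107 needs a rate there about 4 to 11 times that of all other KPWA patients. Taking 0.045% softens this to about 3 to 7.5 times, and to 1.8 at k = 1.5. Such a contrast is possible, because primary care attenders may differ, but the plan does not state it.
- **The value of k is unknown.** A reader might infer that the trial can detect only a doubling or more. The documents do not support that: the re-solved effect reaches +100% only at k of about 1.96, and at k = 1.5 it is +85%.
- **The plan sets no relative target.** The 67% is simply 2.6/3.9. A reader might infer that 2.6 is out of reach; on the annual reading it is the reverse, because power for that absolute increase is higher than stated.

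It is also fair that all non-pilot primary care clinics were included, so this calculation did not set the number of sites, and that a null result would be read from the confidence interval too. What remains is an unlabelled base rate for a primary outcome whose most natural reading conflicts with its use.

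**Conclusion.** The point holds as a probable unit error, not a proven one. It is certain that 3.9 per 10,000 was used per patient-month and that no period or conversion is documented. It is likely, from the matching year, measure family and value, that the figure is annual.

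If it is, the base rate, detectable effects and treatment power table are wrong for any k above 1, always in the same direction. The 80% detectable effect falls in absolute terms from 2.6 to between 2.22 and 1.52 per 10,000, and rises in relative terms from about 67% to between 85% and 156%, for k from 1.5 to 4. The size within that range rests wholly on the assumed k. The test and the estimate are untouched, and the brief-intervention figures are not affected by this point.

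**What to change.** Replace 3.9 per 10,000 with the observed 28-day pre-launch rate of the treatment outcome at these 19 sites, using data from January 2015 and the same outcome algorithm. Restate the 80% and 90% detectable effects and the treatment power table in both absolute and relative terms. State the period and denominator of the 2014 figure, and reconcile it with the 0.04% per year in the Setting section. If 3.9 does prove to be a monthly, site-specific rate, saying so and explaining the difference from the annual figure would settle the matter.

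The cost is one rerun of a closed-form calculation and rewording of one paragraph in each document, with no extra patients and no change to the design or test. The downside is that, if the rate was annual, the stated relative detectable effect becomes less favourable.

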## Descriptive analyses

### Descriptive statistics

We will generate summary statistics on the number of visits per person to a site during a monthly period. At the patient level, we will describe demographic characteristics and clinical variables across patients with a visit to a clinic in the pre-implementation period and patients with a visit in the post implementation period. For time-varying disease status variables (e.g., the presence of a documented diagnosis), characteristics will be summarized based on whether the patient had the disease documented at any visit during the period (pre- or post-implementation), as well as based off of the patient's first visit during the period. Additionally, as suggested by the CONSORT extension for stepped wedge trials (Hemming et al. 2018), clinic and patient-level variables will be described by allocated sequence (i.e., study wave).

### Crossover

We will examine the proportion of visits in which the patient visited a site during the pre-implementation period after having had a prior visit, to a different site during that site's post-implementation period (main measure). Additionally, as a general measure of crossover across sites, for each site we will compute the proportion of patients who had a visit at that site who also had a visit at each of the other sites. As a measure of crossover across the implementation periods, we will compute the proportion of patients who had a visit both before and after the launch date, overall and by site.

### Graphical analysis of study outcomes

To visualize how the study outcomes change over time within a site, as well as pre- versus post-implementation, we will plot the site-specific, crude (unadjusted) rates of the study outcomes as a function of study month.

### Primary analysis

Following the general framework for analyzing data from a stepped-wedge trial (Hussey and Hughes 2007; Hughes et al. 2015), for each outcome described above we will apply the following logistic mixed-effect model (GLMM),

$$\text{logit } P(Y_{ijm} = 1) = \alpha + \beta \text{Int}_{jm} + \gamma S_j + f(cm) + b_j + u_i,$$

where  $Y_{ijm}$  is the outcome for person  $i$  who visited site  $j$  in time interval  $m$ . As described above, the intervals used in analyses are 28-day periods ("months" hereafter) before and after the launch date for each clinic. The term  $\text{Int}_{jm}$  is an indicator variable for whether site  $j$  was in the post- versus pre-implementation period as of that month. The term  $S_j$  is an indicator for whether site  $j$  was a Y2 site versus a Y1 site (stratification variable), which accounts for possible differences in the outcome across these two years of sites (Y1 and Y2), and  $f(cm)$  is a pre-specified function of calendar month to account for the potential for a secular trend in outcome rates over time. We plan to model  $f(cm)$  using indicator variables for each 4-month calendar period. Alternate specifications will be considered in a sensitivity analysis (details below). Additionally,  $b_j \sim N(0, \tau_b^2)$  is a site-level random effect to account for correlation of individuals from the same site and  $u_i \sim N(0, \tau_u^2)$  is a person-level random effect to account for correlation of outcomes from the same individual, since a person can have a visit at multiple sites in the same or different month, or at the same site over multiple months.

The primary comparison (1) described above will be evaluated by first conducting a two-sided Wald test (at the 0.05 level) of the coefficient  $\beta$ . Ninety-five percent Wald confidence intervals (95% CI) for  $\beta$  will also be calculated.

For descriptive purposes, from the model, we will estimate the marginal predicted probability of the outcome in the pre- and post-implementation period by averaging over covariate distribution and the random effects.

To test the contrasts for secondary time periods of interest, the term  $Int_{jm}$  will be replaced with a categorical variable for whether the month was in the pre-, active implementation, or sustainment period, and the relevant coefficient will be tested. For example, for testing whether there was a difference in the outcome rates in the active versus pre-implementation period, we will test the null hypothesis that the coefficient for the indicator for the active implementation period (versus the pre-period) is equal to zero. As above, from the model we will estimate the marginal predicted probability (and 95% CIs) of the outcome for each of the implementation periods.

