To evaluate the impact of the SPARC intervention on sustained receipt of evidence-based alcohol-related care, we are conducting a pragmatic stepped-wedge trial in 22 KPWA PC clinics (Fig. 3). A stepped-wedge approach [68] was chosen so that all clinics would eventually receive the intervention and because providing practice coaches for more than four clinics at a time was not feasible. The trial has seven waves staggered by 4 months, such that the final 2 months of the active implementation phase of one wave overlaps with the preparation phase of the next wave. The sample for the study is patients 18 years of age and older who have a PC visit in one of the 22 participating clinics during the study period.

Fig. 3

SPARC stepped-wedge pragmatic clinical trial design. *Usual care start: January 1, 2015. **Data collection end date: July 31, 2018. Twenty-two clinics (with three paired to create 19 randomized clinical sites total) were randomized across seven waves with stratification (three waves year 1 and four waves years 2–3). Clinics in square bracket are paired as one site.

Randomization

Stratified randomization was used, with 9 clinics randomized in year 1 (three sites in each of three waves), and the remaining 13 clinics randomized in years 2–3 (Fig. 3). Clinics randomized in year 1 are referred to as Y1 sites and those randomized in years 2–3 as Y2 sites. The random assignment to study wave within Y1 and Y2 was generated using a computer-generated list of random numbers by the study biostatistician after all sites were recruited. An additional file describes our randomization scheme and rationale in detail [see Additional file 1].

Four phases of the SPARC trial

Figure 2 shows the four phases of implementation in each clinic. As above, each clinic has approximately 6 months of support from practice coaches, including up to 8 weeks in the “preparation” phase, before the official launch date of SPARC/Behavioral Health Integration,

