## Randomization

As discussed above, randomization was to be stratified on the study year of implementation (Y1 vs. Y2). The 9 Y1 sites were randomly assigned to begin active implementation in one of 3 waves (3 sites per wave). Within Y2, the 4 implementation waves were to consist of 2 waves with 3 sites each, and 2 waves with 2 sites each. Given the requirements above that the last wave have just two sites and that one Y2 site needed to be in a wave with just one other site (we will refer to this site as site A), we developed a randomization scheme to ensure that each site had the same probability of being assigned to each wave (0.2 probability to be assigned to Y2 wave 4 and 0.8/3 each for waves 1-3 of Y2) as follows. First, we randomly selected one of the first 3 waves to be the other 2-site wave. Then, we randomly assigned site A to wave 4 with probability 0.2 or to the other 2-site wave with probability 0.8. The remaining 9 Y2 sites were then to be randomly assigned to the other available slots. Under this randomization scheme, letting B denote an arbitrary site different from site A, we have:

- $P(\text{site A assigned to wave 4}) = 0.2$
- $P(\text{site B assigned to wave 4}) = P(\text{site B assigned to wave 4} \mid \text{A assigned to wave 4}) * P(\text{A assigned to wave 4}) + P(\text{site B assigned to wave 4} \mid \text{A not assigned to wave 4}) = 1/9 * 0.2 + 2/9 * 0.8 = 0.2$
- $P(\text{site A assigned to wave } j) = P(\text{wave } j \text{ assigned to be the other 2-site wave}) * P(\text{site A assigned to wave } j \mid \text{wave } j \text{ assigned to be the other 2-site wave}) = 1/3 * 0.8, \text{ for } j = 1, 2, 3$
- $P(\text{site B assigned to wave } j) = 1/3 * [1 - P(\text{site A assigned to wave } j)] = 0.8/3, \text{ for } j = 1, 2, 3$

[figure not shown]

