## Allocation concealment

The random allocation sequences were generated by the study biostatistician ([name]) after all of the KPWA sites were identified, including the pairing of clinics within 3 of the sites. Y1 sites were randomized to waves on January 22, 2016 and Y2 sites were randomized on October 7, 2016. The assigned waves are shown in **Table 1** below.

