## SPARC Implementation stages

Implementation time windows of interest are shown in **Figure 2**. The “preparatory period” is defined as the period 2 months prior to the SPARC launch date up until the launch, and the “active

implementation” period is defined as the period from 1-4 months after the SPARC launch date at a given site. We will refer to the period up to and including the preparatory period as the “pre-implementation” period, and the period starting with the launch date as the “post-implementation” period. Following intention-to-treat principles, unless otherwise specified, these pre- and post-implementation periods will be defined based on the launch dates during which active implementation was planned to occur (shown in **Table 1**), rather than the actual date when the site begins implementing SPARC (if implementation was delayed).

**Table 1.** Implementation wave dates and randomized assignments of sites to waves

Year	Wave	Site (masked)	Launch Date
Y1	1	Site A	April 4 th , 2016
Y1	1	Site B	April 11 th , 2016
Y1	1	Site C	April 18 th , 2016
Y1	2	Site D	September 7 th , 2016
Y1	2	Site E	September 12 th , 2016
Y1	2	Site F	September 19 th , 2016
Y1	3	Site G	January 4 rd , 2017
Y1	3	Site H	January 9 th , 2017
Y1	3	Site I	January 16 th , 2017
Y2	4	Site J	April 24 th , 2017
Y2	4	Site K	April 24 th , 2017
Y2	4	Site L	April 24 th , 2017
Y2	5	Site M	August 14 th , 2017
Y2	5	Site N	August 14 th , 2017
Y2	5	Site O	August 14 th , 2017
Y2	6	Site P	December 4 th , 2017
Y2	6	Site Q	December 4 th , 2017
Y2	7	Site R	April 9 th , 2018
Y2	7	Site S	April 9 th , 2018

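### About a third of the information on the primary effect is a Y1-versus-Y2 comparison that was not randomised, with no stratum-by-time analysis named; separately, the Protocol's month and period counts do not fit the study span

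*SAP*

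**What the plan says.** **Strata.** Under Stepped-wedge trial design, the SAP says "the health system identified 9 sites that would be randomized in Year 1 (3 sites in each of 3 waves"). Ten other sites were left for the later waves and form Y2. Under Randomization it adds that "The 9 Y1 sites were randomly assigned to begin active implementation in one of 3 waves"; the ten Y2 sites were allocated among four later waves. The two allocations took place at different times: "Y1 sites were randomized to waves on January 22, 2016 and Y2 sites were randomized on October 7, 2016" (SAP, Allocation concealment).

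**Clinics.** The Protocol's Randomization section counts clinics: "with 9 clinics randomized in year 1 (three sites in each of three waves), and the remaining 13 clinics randomized in years" (the second and third). Nine clinics make nine Y1 sites and thirteen clinics make ten Y2 sites, so all three paired sites are in Y2.

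**Launch dates.** SAP Table 1 ("Implementation wave dates and randomized assignments of sites to waves") puts Y1 launches between 4 April 2016 and 16 January 2017 and Y2 launches between 24 April 2017 and 9 April 2018.

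**Model.** Both documents give the same logistic mixed model: an intervention indicator, a stratum indicator S_j, one function f(cm) of calendar month, and site and person random intercepts. S_j is the term "which accounts for possible differences in the outcome across these two years of sites (Y1 and Y2"). The SAP uses an indicator for every 4-month calendar period and does not count them. The Protocol (Statistical analysis) numbers the months 1 to 31 and counts seven 4-month periods, while giving the span as January 2015 to July 2018.

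**Checks.** The SAP says that details of alternate f(cm) specifications follow, but none appear in the text available. The Protocol refers other sensitivity analyses to an additional file that is not among the documents. The SAP also plans crude site plots by month, and "clinic and patient-level variables will be described by allocated sequence (i.e., study wave").

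**The concern.** Randomisation justifies comparing early with late waves inside Y1, and early with late waves inside Y2. It does not justify comparing Y1 with Y2, and every Y1 launch precedes every Y2 launch. From 16 January to 23 April 2017 (16 + 28 + 31 + 23 = 98 days) all Y1 sites are post-launch and all Y2 sites are pre-launch.

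Because f(cm) is common to both strata, the model treats that contrast as evidence on beta. If the outcome was drifting differently in Y2, part of the drift enters the effect estimate. S_j cannot absorb it because S_j does not vary over time. Both co-primary results are affected, and nothing in the text available would show a reader how far the estimate depends on the assumption.

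The month and period counts are a separate matter. They specify the primary model's time term, and as written they cannot be applied to the stated span.

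**Working it through.** **1. Reproducing the SAP's power figure.** Inputs (SAP, Power calculations): 19 sites in waves of 3, 3, 3, 3, 3, 2, 2; 4 months between waves, hence T = 8 periods; 1,205 × 4 = 4,820 patients per site-period; ICC 0.001; brief intervention (BI) rate 34.2 per 10,000. With X the post-launch indicator, U = ΣX = 81, W = Σ(period totals)² = 1,145 and V = Σ(site totals)² = 415. The Hussey-Hughes variance is

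Var(beta) = I σ²(σ² + Tτ²) / [(IU − W)σ² + (U² + ITU − TW − IV)τ²],

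with I = 19, IU − W = 394 and U² + ITU − TW − IV = 1,828. At the mean rate (34.2 + 41.3)/2 = 37.75 per 10,000, p(1 − p) = 0.003761, so σ² = 0.003761/4,820 = 7.80e-7 and τ² = 0.001 × 0.003761 = 3.76e-6. This gives SE = 2.52e-4, and 2.80 × SE = 7.07 per 10,000 (stated: 7.1). Treatment gives 2.63 (stated: 2.6). The stated power holds for the model it assumes.

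**2. Splitting the information in that design.** All terms share the factor 1/[σ²(σ² + 8τ²)], and σ² = τ²/4.82 = 0.2075τ².

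- Common periods, no S_j: (394σ² + 1,828τ²)/19 = 20.74σ² + 96.21τ² = 100.5τ².
- Adding S_j removes (27 − 81 × 10/19)²/(8 × 90/19) = 6.45 units of σ², leaving 99.2τ².
- S_j × period makes the strata separate designs whose information adds: (36σ² + 234τ²)/9 for Y1 plus (61σ² + 367τ²)/10 for Y2 = 10.1σ² + 62.7τ² = 64.8τ².

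Between-stratum share = 1 − 64.8/99.2 = 0.347.

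**3. Actual dates.** Generalised least squares with Table 1 launch dates, 1 January 2015 to 31 July 2018 (1,308 days, 11 periods), 1,205 patients per site per 28 days and ICC 0.001:

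| | SE of log OR, common f(cm) | SE, S_j × period |
|---|---|---|
| BI, 34.2 per 10,000 | 0.0625 | 0.0781 |
| Treatment, 3.9 per 10,000 | 0.185 | 0.231 |

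The SE ratio is 1.2496, so the share is 1 − 1/1.2496² = 0.360. It does not depend on the base rate.

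**4. Varying what the documents do not fix.**

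| Assumption | Share |
|---|---|
| ICC 0.0001 to 0.05 | 35–36% |
| Three paired Y2 sites twice the size of the others (all 120 placements) | 33–38% |
| Site-size CV 0.5 (central 95% of 300 draws) | 33–41% |
| Person correlation 0.1–0.5, patient overlap 10–40% between months | 26–36% |

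**5. What the planned plots can show.** All 19 sites share 459 pre-launch days (1 January 2015 to 3 April 2016), or 1.257 years. A site-month expects 1,205 × 0.00342 = 4.1 BI events and 1,205 × 0.00039 = 0.47 treatment events; exp(−0.47) = 0.63 of site-months have no treatment event. Pooled expected events are 608 (Y1) and 676 (Y2) for BI, and 69 and 77 for treatment. The SE of the difference in log-odds slope is sqrt[(1/e1 + 1/e2)/(1.257²/12)] = 0.154 (BI) and 0.456 (treatment) per year. Multiplied by 2.80 and exponentiated, the difference detectable with 80% power is an OR of about 1.5 per year (BI) or 3.6 per year (treatment).

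**6. Illustration of bias (assumed drift, no basis in the documents).** If Y2 log odds drift linearly relative to Y1 and there is no true effect, beta shifts by −5.03 × the monthly slope. At 10% per year, −5.03 × ln(1.10)/12 = −0.040, an OR of 0.961. That is 0.64 SE for BI and 0.22 SE for treatment. Drifts of 5–20% per year in either direction give ORs between 0.93 and 1.08.

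**7. Calendar.** January 2015 to July 2018 is 3 × 12 + 7 = 43 months; 43/4 = 10.75, so 11 periods, the last one short. Seven periods cover 28 months, or 32 with a reference period added.

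**The case against.** **The missing analysis may exist.** The additional file is not available, and the SAP's reference list includes works on small-sample inference that its text never cites, so some analysis text may be absent. This stands as a limit: the absence can be asserted only of the text available. The SAP's own pointer still leads to no details and needs completing.

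**The model is not shown to be wrong.** A common time function plus the stratification variable is prespecified. Nothing in the documents shows diverging trends, and the pairing of sites in Y2 is a difference in make-up, not in trend. That stands, and it is why the primary model is kept.

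**The illustrated harm is modest.** At a BI rate of 16.0 per 10,000 (8.9% × 36% × 5%; SE 0.091), the 10% drift amounts to 0.44 SE rather than 0.64. With a January 2016 start, the share falls to 29% and the bias factor becomes +1.45, opposite in sign and about 3.5 times smaller. This supports calling size and sign unknown. It does not displace the January 2015 start, which the Protocol's design figure note and Statistical analysis section and the SAP's Study sample section all give.

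**A cheaper term is available.** S_j × linear time keeps about 95% of the information and removes linear drift. It would not confine beta to the randomised within-stratum comparisons, which is the purpose of the check.

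**The Protocol's counts agree with each other.** Months 1 to 31 match January 2016 to July 2018, which needs eight 4-month periods, hence seven indicators and a reference. That is a plausible origin, but it contradicts the span given in the same sentence.

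**Conclusion.** Both points hold. Roughly one third of the information on beta comes from groups that were not randomised against each other: 36% with Table 1 dates and equal site sizes, and 26–41% across the assumed site sizes and person correlation. Varying the start date, period width and weighting gives about 27–43%. These figures come from a linear working approximation, not from a fit of the logistic mixed model.

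The consequence is reliance on parallel trends, not demonstrated bias. The concern is mainly for BI, where a given drift is larger relative to the SE. The planned plots could reveal a large divergence between strata but not a modest one.

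The calendar counts are an error in the Protocol only. The SAP's wording fits the full span.

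**What to change.** 1. Keep the primary model. Where the SAP promises alternate time specifications, prespecify one sensitivity analysis that replaces f(cm) with S_j × 4-month-period indicators, and report it beside the primary result for both co-primary outcomes. State in advance that its SE is expected to be roughly a quarter larger (approximate).
2. In the Protocol's Statistical analysis section, change the time term to 43 months and 11 four-month periods, in line with the SAP.

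The cost is wording in both documents and one extra model fit per outcome. The primary analysis loses no power. On the 8-period power design, the sensitivity analysis has an 80% detectable effect of about 8.9 per 10,000 for BI (against 7.1) and 3.4 for treatment (against 2.6). It uses 2 × 11 = 22 time-and-stratum parameters instead of 11 + 1 = 12. At base rates each full stratum-period expects about 18 (Y1) or 20 (Y2) treatment events, so it should be estimable.
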